6. STUDY PROCEDURES

6.1 Schedule of Evaluations

Study Assessments. See Table 1. Besides the study related procedures, standard clinical care will be provided pre and post hysterectomy or myomectomy to the study participants.

6.2 Visit Description

6.2.1 Scheduled Visits

For the timing of each visit, see Table 1. Site personnel will determine the start of each treatment period and the participants will be informed about the visit dates.

Visit 1: Screening visit

The following procedures will be performed during this visit:

- Informative discussion about the study and obtaining of the informed consent.
- Obtain signed and dated informed consent.
- Subject identification number assigned.
- Assess inclusion/ exclusion criteria.
- Demographic data, smoking history, and alcohol consumption.
- Medical, reproductive, menstrual, and fibroids histories.
- Prior and concomitant medications the subject is taking.
- Information about adverse events assessment.
- Physical examination, gynecological examination.
- Vital signs.
- Urine pregnancy test.
- Pap smear (may be waived if a normal result has been documented in the subject's medical record within the previous 12 months).
- Endometrial biopsy if not done in the last 12 months.
- Ultrasound for fibroid location, size, and MRI only if the ultrasound is inconclusive.
- Laboratory evaluations: CBC with differential, hemoglobin, hematocrit, ferritin, liver enzymes and lipid panel. Urine pregnancy test.
- Instruct the subject to complete the questionnaires.

Visit 2: Drug intake initiation visit

If the subject is eligible for the study based on the screening visit information, the subject will be invited to come for the second visit.

The study subjects will be randomized into 12 weeks of simvastatin (40 mg/day orally) or placebo arms (1:1). We will use stratified block randomization with randomly permuted blocks of sizes 4 and 6 into one of the two arms.

The randomization scheme will be stratified by race/ethnicity in three categories: African American, Caucasian, and Hispanic. All other races will be excluded (small numbers precludes proper stratification and analysis). The stratification will ensure similar distribution of

race/ethnicity categories across the arms. This is a double-blinded study, neither subjects nor interacting personnel will know arm designation.

This is an “add-on” study, i.e. subjects in both arms will continue their current treatments excluding hormonal contraceptives and medications contraindicated as per prescribing information for simvastatin.

The study medication will be dispensed through the Investigational Drug Pharmacy at Johns Hopkins. The subject will be informed about the medication intake. The study medication is an oral tablet to be taken once a day in the evening at the same time. The dose of the simvastatin group is 40 mg/ day.

The restricted foods such as grapefruit, cranberry juice, and dietary supplements will be discussed with the subject.

At one time the participant will be provided medication for 6 weeks. The study nurse will contact the participant every week at the participant’s preferred time to ensure compliance and monitor any adverse events that may occur after starting the intake of the medication.

Visit 3 and 4: At 6 and 12 weeks from Drug Initiation Visit

Visits 3, and 4 will be at 6 and 12 weeks after the initiation of the study drug. These will occur at Johns Hopkins outpatient clinic to follow up with the study participant at intervals throughout the study duration of 12 weeks.

There will be review of concomitant medications that the subject is taking and an adverse events assessment at each visit. The restricted foods such as grapefruit, cranberry juice, and dietary supplements will be discussed with the subject.

The study questionnaires will be filled at visit 4. The subject will be informed about the ultrasound result at 12 weeks, and counselled about the need for surgery if there are significant changes in fibroid size.

Follow up Visit

The participant will have their scheduled hysterectomy or myomectomy and the fibroid sample will be collected and evaluated for histologic effects of simvastatin on fibroids.

The standard clinical care follow up will be provided to the subject by their gynecologists.

The study team will follow up with the subjects after their surgery at their 2 and 6 weeks post-surgery visits to monitor for any adverse events. The subjects will fill the final questionnaires for the study at the 6 week post surgery visit.

6.3 Study Outcomes

The primary outcome will be to assess the preliminary clinical efficacy of simvastatin in reducing size of fibroids. The study will also evaluate the effects of simvastatin on fibroid related symptoms. This will be done by collection of data on symptoms and health related quality of life as obtained through questionnaires and by maintaining a daily log of symptoms on a subject diary during the treatment period of the study.

For the safety outcomes, the study will evaluate the percentage of adverse events (AE) and serious adverse events (SAE) by organ systems, including signs/symptoms, laboratory values, and clinical events.

We will also compare hemoglobin, hematocrit, ferritin, liver enzymes and lipid panel pre and post-study.

For the secondary objectives to characterize the molecular, cellular and histologic effects of simvastatin on human fibroids, the tissue will be characterized using TUNEL and immunoblotting techniques.

6.4 Blood sampling

15-20 mL blood will be obtained for CBC with differential, hemoglobin, hematocrit, ferritin, liver enzymes and lipid panel pre and post study duration to compare the results at baseline and end of study.

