2.3 Safety Objectives

- 2.3.1 Percentage of adverse events (AE) and serious adverse events (SAE) by organ systems, including signs/symptoms, laboratory values, and clinical events.
- 2.3.2 Lab: We will compare hemoglobin, hematocrit, ferritin, liver enzymes and lipid panel pre and post study.

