3.2 Sample Size Determination

We plan to enroll 60 study participants (30 in each arm). With a 20% anticipated withdrawal rate (from prior experience in similar studies), we plan to recruit 72 subjects. Sample size was estimated based on pre-clinical results of tissue effect where we expect a difference of 0.2 (20% effect size). This is a pilot study, and based on a 20% effect size and ability to measure within 0.5 centimeter (sigma) with an alpha of 0.5 and power of 0.8, the sample size is 50 subjects using a two sided t-test. We will enroll 60 subjects, to be conservative, which provides confidence that we will observe a difference, if one exists.

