We do not anticipate having a participant in this study who will have an unexpected diagnosis of leiomyosarcoma. We will keep all tissue sections and samples until the final pathology report is made and are capable of returning tissue to the pathologist for evaluation, if necessary. Even when the patient has had a hysterectomy or myomectomy, the collected fibroid itself is not manipulated at the time of surgery, minimizing any untoward cell spillage into the peritoneal cavity. In the highly unlikely event that we do enroll a subject with the final pathological diagnosis of leiomyosarcoma we will treat this as a serious adverse event and report it immediately.

A double blinded, phase II, randomized controlled trial to study the effects of simvastatin in patients with uterine leiomyoma.

The subjects will be scheduled to undergo surgery within 1 week following the 12 weeks treatment period of the study.

Standard clinical care will be provided pre and post hysterectomy/ myomectomy to the participants independent of the study assessments. The study nurse will follow up with the study participants during their 2 and 6 weeks post-operative visits with the subject's gynecologist.

More detailed information about the study visits and study related procedures is shown in Figure 1 and Table 1 below.

Study Design: Flowchart of the study design can be seen in Figure 1 below.

A double blinded, phase II, randomized controlled trial to study the effects of simvastatin in patients with uterine leiomyoma.

[figure not shown]

Figure 1: Study design flowchart.

Table 1: Detailed Flowchart of Study Assessments

A double blinded, phase II, randomized controlled trial to study the effects of simvastatin in patients with uterine leiomyoma.

Visit	Visit 1	Visit 2	Visit 3	Visit 4	Follow up Visit
Activity	Screening	Beginning of the treatment period	6 weeks after start of treatment period	12 weeks after start of treatment period	Scheduled at 2 and 6 weeks post surgery
Informed Consent	X				
I/E criteria	X				
Demographics	X				
Smoking/Alcohol History	X				
Medical History	X				
Reproductive, menstrual, fibroid history	X				
Medication reconciliation & restricted food discussion	X	X	X	X	
Vital signs	X	X	X	X	
Physical examination	X			X	
Gynecological exam	X			X	
Cervical smear	X				
Ultrasound examination	X			X	
Endometrial biopsy	X				
Labs	X			X	
Inform about contraception	X	X	X	X	

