8. CRITERIA FOR INTERVENTION DISCONTINUATION

Subjects will only receive the study drug simvastatin or placebo as a participant of the research study. Subjects may voluntarily withdraw from the study at any time and for any reason. The investigator may discontinue the subject's participation in the study if he believes it necessary for any reason including:

- 8.1 Intercurrent pregnancy
- 8.2 Symptom improvement where surgery is not necessary
- 8.3 Occurrence of an adverse event that precludes further participation in the study at the discretion of the investigator
- 8.4 Clinically significant adverse results in laboratory testing
- 8.5 Failure to comply with the protocol
- 8.6 Evidence of significant, persistent side effects

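### Blood tests are planned only at screening and Visit 4, with no draw at early stopping, so women who leave early have no planned on-drug value for the lab comparison in 2.3.2

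*Protocol*

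**What the plan says.** - **Objective.** Section 2.3.2: "We will compare hemoglobin, hematocrit, ferritin, liver enzymes and lipid panel pre and post study".
- **Timing of the draws.** Section 6.4 says blood is taken "pre and post study duration to compare the results at baseline and end of study". In section 3.4, under "Table 1: Detailed Flowchart of Study Assessments", the Labs row is marked at Visit 1 (screening) and Visit 4 (12 weeks after treatment starts) and nowhere else. The descriptions of Visits 2 and 3 in section 6.2 list no blood tests.
- **Early stopping.** Section 8 allows voluntary withdrawal at any point. It also lets the investigator end a woman's "participation in the study if he believes it necessary for any reason including" six listed grounds. Three bear on safety: an adverse event that the investigator judges to rule out her staying in (8.3), lasting side effects (8.6), and, under 8.4, "Clinically significant adverse results in laboratory testing". No exit visit or exit draw is attached to any of them.
- **Analysis.** Section 9 names lab values among the continuous outcomes modelled with a Gaussian GLM and sets a 12-week focus. It adds a mixed model over entry, week 6 and week 12, and sensitivity analyses for drop-out.
- **Expected losses.** Section 3.2: "With a 20% anticipated withdrawal rate (from prior experience in similar studies), we plan to recruit 72 subjects".

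**The concern.** Section 8 ends participation in the study, not only dosing, so a woman who leaves before week 12 has no later visit at which blood would be taken. Some of the listed grounds for leaving are side effects or laboratory findings, and section 3.6 counts liver function abnormalities among the known side effects of simvastatin. The women whose on-drug liver enzymes would be of most interest can thus be among those with no planned measurement.

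At stake is the completeness of a stated safety objective. The primary outcome, fibroid size, is not touched. A value not drawn when a woman stops cannot be recovered later, and a schedule of blood draws belongs in the protocol, so a separate analysis plan could not fill the gap.

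**Working it through.** **1. Is an on-drug lab planned anywhere before Visit 4?** The places that could hold one, side by side:

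- Table 1 and section 6.4: two draws, screening and Visit 4.
- Section 6.2, Visits 2 and 3: medication review, adverse events, dispensing and counselling; no labs.
- Section 7: care for adverse events, which may include tests, but none is specified.
- Section 8: no exit assessment.
- Section 10: documentation of adverse events and withdrawals; no added measurement.

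None is planned.

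**2. Can the analysis supply the value?** The mixed model uses week 6, but no week-6 lab is drawn, so an early leaver contributes at most her screening value. Multiple imputation in section 9 is for covariates. The drop-out sensitivity analyses can vary what is assumed about a missing value but cannot measure it.

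**3. Who is left without a value?**

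- A woman with a symptom-free enzyme rise who stays in is measured at Visit 4.
- A woman who stops the capsules but stays in keeps her Visit 4 draw, which may then be off drug.
- A woman removed under 8.4 during treatment must have had an unscheduled test. Its result can count under 2.3.1, which covers adverse events "including signs/symptoms, laboratory values, and clinical events".
- A woman who leaves for symptoms and is tested during her care is in the same position.
- A woman who leaves early and untested has no on-drug value at all.

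**4. How many could leave early?** The plan gives no count of missing labs to reproduce. Its recruitment figure is 60 × 1.20 = 72. The synopsis and sections 3.3.1 and 3.3.2 describe 60 randomized women (30 per arm), while section 3.2 recruits 72, so both totals are shown. With N women and withdrawal rate w, N × w lack the planned value and N × (1 − w) have it:

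| N | w | Without value | With value |
|---|---|---|---|
| 60 | 0.20 | 12 | 48 |
| 72 | 0.20 | 14.4, about 14 | 57.6, about 58 |

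If losses split evenly between the arms (assumed), about 24 per arm have a value in the first case and about 29 in the second. Over an assumed range of 10% to 30% around the stated 20%, the number without a value is 6 to 18 of 60, or 7.2 to 21.6 of 72.

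These counts cover withdrawal for any cause and take every exit to precede Visit 4. Women who decide against surgery after the week-12 ultrasound already have their labs, so the number may be lower. The 20% is only what the protocol expects, so it may also be higher.

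**The case against.** The strongest reply is that the safety signal from early leavers is largely kept elsewhere. Section 7 has every woman followed weekly. It also defines serious adverse events so broadly that a side effect unrelated to surgery or fibroids goes on the serious adverse event form. Section 9 tabulates adverse events by arm and reports drop-out patterns, and section 10 singles out withdrawals related to adverse events for documentation. This stands: what is lost is a continuous lab value in a non-primary comparison.

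A reader might infer that the liver-enzyme difference will be understated. The documents do not support that. If leaving is unrelated to lab values, the bias is zero. Understatement would need women with raised enzymes to leave untested, and more often on simvastatin than on placebo, and nothing in the protocol says how common that is. No direction follows for hemoglobin, hematocrit, ferritin or lipids either. Muscle effects, among the most important risks in section 3.6, are not measured by this panel.

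The end of study in section 6.4 could also be read as each woman's own end. Table 1 ties the draw to week 12, and if the looser reading was meant, one sentence would settle it.

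Finally, this is a pilot, and its sections agree with each other on a before-and-after design. That stands too and limits the severity, but it does not remove a gap that can be closed cheaply.

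**Conclusion.** The point holds as a minor improvement to the design. Early leavers, including those who leave because of side effects, have no planned on-drug value for 2.3.2, and no analysis in section 9 can supply one. At the anticipated 20% withdrawal that is about 12 of 60 or about 14 of 72 women, depending on how many are randomized and assuming that all exits come before Visit 4. Some of these women may have unscheduled results from adverse-event care. The protocol does not allow the size or direction of any bias to be derived, and none is claimed. The schedule facts are certain; the practical importance is modest.

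**What to change.** Add to sections 6.4 and 8, with a footnote to Table 1:

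> Any woman who stops study drug or leaves before week 12 is asked to have the planned post-study blood draw when she stops, as close to the last dose as possible, unless she declines. Women who stop study drug but remain in the study also keep the Visit 4 draw.

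Keep the week-12 comparison as planned. Add one supplementary safety table by arm showing the last on-drug lab value (early-stop or week 12) with time on drug.

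**What it does not do.** The week-12 comparison will still cover only women who reach Visit 4. The new table sits beside it and does not complete it.

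**Cost.** A few sentences, a footnote and a table. For a woman who leaves, the planned draw is taken earlier, with one short contact. For a woman who stops drug but stays, it is one extra draw of 15-20 mL. Early-stop values will come at varying times on drug, which is why they should not be pooled with the week-12 values. Some women will decline, and some may already be off drug when drawn. The amendment helps only women who leave after it takes effect.

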6.5 Special Instructions and Definitions of Evaluations

A double blinded, phase II, randomized controlled trial to study the effects of simvastatin in patients with uterine leiomyoma.

Fibroid tissues will be collected after hysterectomy or myomectomy and fixed in formalin or snap-frozen. Tissue sections will be analyzed for apoptosis (i.e. by TUNEL) and for effects of simvastatin on ECM production and synthesis using immunoblotting techniques.

7. MANAGEMENT OF ADVERSE EXPERIENCES

Although there are no anticipated serious adverse events associated with this protocol, the subjects will be monitored weekly for any side effects of simvastatin. They will be educated about risks and warning signs, and instructed to call immediately if they believe they are having a reaction or adverse event.

If any adverse event does occur, regardless of who is responsible for the costs, immediate necessary care for adverse events will be provided at Johns Hopkins. As in all clinical trials at Johns Hopkins, adverse events are monitored, addressed and handled most expeditiously.

For this study, serious adverse events are defined as any adverse event not relating to surgery complications, or the presence of fibroids, such as bleeding. All serious adverse events, either observed by the physicians, nurses or reported by the subject, will be recorded on the Johns Hopkins Serious Adverse Event Case Report Form.

The FDA, via form 3500A, and the institutional IRB will be notified in a written IND safety report of any adverse experience that is both serious and unexpected if there is evidence to suggest a causal relationship between the drug and the adverse event. In each written IND safety report, the sponsor will identify all safety reports previously filed with the IND concerning a similar adverse experience, and will analyze the significance of the adverse experience in light of previous, similar reports. Telephone report: FDA will be notified by telephone of any unexpected fatal or life-threatening experience associated with use of the drug in the clinical studies conducted under the IND no later than 3 working days after receipt of the information. Each telephone call to the FDA shall be transmitted to the Center for Drug Evaluation and Research, which has responsibility for review of the IND. For purposes of this section, life-threatening means that the subject was, in view of the investigator, at immediate risk of death from the reaction as it occurred, i.e., it does not include a reaction that, had it occurred in a more serious form, might have caused death. For example, drug induced hepatitis that resolved without evidence of hepatic failure would not be considered life threatening even though drug-induced hepatitis can be fatal.

A double blinded, phase II, randomized controlled trial to study the effects of simvastatin in patients with uterine leiomyoma.

All other anticipated or unanticipated adverse events not considered as serious adverse events will be reported to the FDA and IRB at the time of annual reports. The investigator will review accumulated adverse events after 30 subjects have completed the study, or earlier if the investigators notice any trend in complaints or abnormal laboratory results.

We plan to conduct first interim analysis after 30 subjects complete the study and if the results are sufficient to establish the primary hypothesis, safety and efficacy of the study drug, the study may be discontinued.

For all serious and/or unexpected adverse events, the PI will forward a copy of the adverse event report to the IRB and the FDA for the protocol.

Expected adverse events, (i.e., those events included as potential risks in the consent form) which are not serious, will be reported yearly on the Annual Progress Report (APR) for each protocol. A summary of all serious or unexpected side effects also will be included in the APR. If there were no adverse events, this will be stated in the APR. All serious adverse reactions occurring during the study, either observed by the physicians, nurses or reported by the subject, will be recorded on the Johns Hopkins Serious Adverse Event Case Report Form.

Potential risks are primarily those of simvastatin. We will counsel all study candidates about potential side effects of simvastatin as per prescribing information (1). The most important ones are muscle side effects such as muscle pain, tenderness, weakness or the more serious rhabdomyolysis. Other side effects include gastrointestinal (GI) side effects, liver function abnormalities, allergic reactions, headache, confusion, memory problems, fever, joint pain, cold symptoms, skin rash and sleep problems. The full list of side effects will be discussed at length with potential study candidates before signing of the consent form.

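### The protocol's only general definition of a serious adverse event sorts events by presumed cause, so as written mild drug effects count and serious surgical or fibroid events do not

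*Protocol*

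**What the plan says.** The definition is in Section 7: "serious adverse events are defined as any adverse event not relating to surgery complications, or the presence of fibroids, such as bleeding". It is introduced as the definition for this study. The same section opens with "Although there are no anticipated serious adverse events associated with this protocol" and later requires that "All serious adverse events, either observed by the physicians, nurses or reported by the subject, will be recorded" on the institution's SAE form.

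Three other places touch on seriousness, and none gives a general definition:

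- Section 3.4 says of an unexpected final diagnosis of leiomyosarcoma that "we will treat this as a serious adverse event and report it immediately". This covers one diagnosis.
- Section 7 explains one term for reporting to the FDA: "For purposes of this section, life-threatening means that the subject was, in view of the investigator, at immediate risk of death". The term is used for the telephone report, which covers "any unexpected fatal or life-threatening experience associated with use of the drug".
- Section 10 lists adverse event definitions among the topics to be described, but supplies none.

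The SAE percentage by organ system is a safety outcome in the Synopsis (Safety parameters), Section 2.3 and Section 6.3.

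**The concern.** An SAE definition should separate events by how grave their outcome is. This one separates them by what is thought to have caused them, and it can fail in both directions. Ordinary drug side effects enter the SAE class because they come from neither surgery nor fibroids. Grave events leave it once someone attributes them to surgery or fibroids.

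The setting makes the second failure foreseeable. Every participant is planned for hysterectomy or myomectomy (Section 4.1), with bleeding or pelvic pain as the qualifying symptoms. Bleeding is the definition's own example, and the drug is being tested for its effect on fibroids. A severe bleed attributed to fibroids would therefore drop out of the SAE count before the arms are compared. Section 10 gives the principal investigator sole responsibility for monitoring events, and the protocol describes no independent check on attribution.

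At stake are a stated safety outcome and the route by which serious events reach the IRB and FDA.

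**Working it through.** The protocol gives no figure to reproduce. The check applies the definition literally to four kinds of event and follows each through the reporting rules in Sections 7 and 11.1.

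| Event | SAE under Section 7? | Reporting consequence |
|---|---|---|
| Mild headache or rash on treatment, not attributed to surgery or fibroids | Yes | SAE form; forwarded to IRB and FDA; IRB notice under Section 11.1 |
| Rhabdomyolysis | Yes | As above, in the same class as the headache |
| Fatal or life-threatening event attributed to surgery or fibroids, expected | No | No SAE form, no SAE-triggered IRB notice; annual report |
| Same event, unexpected | No | Section 7 gives two rules: annual report for unanticipated events not classed as SAEs, and forwarding of unexpected events to IRB and FDA |

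The definition was then compared with the rest of Section 7.

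- The section anticipates no SAEs, yet it lists headache, rash, cold symptoms and sleep problems among the known effects of simvastatin. Under the definition each of these is an SAE. The two statements conflict.
- The section sends expected events that are not serious to the yearly report. Under the definition no drug side effect could belong to that class. This is tension rather than strict contradiction, because the consent form is not shown and may list surgical or fibroid risks that would fill the class.

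Two reporting routes are little affected. The written IND report applies to "any adverse experience that is both serious and unexpected if there is evidence to suggest a causal relationship", so most mild expected effects would not trigger it and most surgical events would not qualify under any definition. The telephone report for unexpected fatal or life-threatening drug-associated events does not depend on the SAE definition.

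**Exposed time.** Inputs: 18-20 weeks in total (Synopsis, Study duration) and post-operative adverse event monitoring to 6 weeks (Section 5.1.3).

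- 6/20 = 0.300 and 6/18 = 0.333, so 30-33% of a woman's time on study if she has the planned surgery.
- Check from the parts: Section 3.4 says "The subjects will be scheduled to undergo surgery within 1 week following the 12 weeks treatment period of the study". Hence 12 + (0 to 1) + 6 = 18 to 19 weeks; 6/18 = 0.333 and 6/19 = 0.316, inside the range.

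No surgical complication in that time can be an SAE. The fibroid exclusion applies throughout.

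**Over-inclusion, by assumption only.** The protocol gives no adverse event rate. If 20% to 50% of the 30 women per arm had only a mild event unrelated to surgery or fibroids, then 0.20 × 30 = 6 to 0.50 × 30 = 15 women per arm would carry the SAE label without serious harm. The conclusion does not depend on this range.

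**The case against.** The strongest reply is that nobody would apply the sentence literally. Elsewhere Section 7 uses the word serious in its ordinary sense: it contrasts muscle pain with the graver rhabdomyolysis and keeps a class of expected events that are not serious. The sentence may be a badly drafted exclusion clause, and the SAE form, which is not shown, may carry its own criteria. In the ordinary sense, the rule forwarding serious or unexpected events would catch a fatal surgical complication. A further sentence in Section 7 puts serious adverse reactions on the SAE form. Another includes serious or unexpected effects in the annual summary as well, which suggests that forwarding and annual reporting may be cumulative.

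Part of this stands. How staff would behave in practice is unknown, and the two routes for unexpected events could be read together, although the protocol does not say so. Surgical complications also remain adverse events, monitored at the 2- and 6-week visits, and the test planned in Section 9 compares adverse events by type without naming SAEs.

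It does not rescue the definition. The ordinary uses of the word show that Section 7 holds two meanings and leave staff to choose between them. The sentence on adverse reactions uses a different term and defines nothing. An unseen form cannot correct an explicit study-specific definition in the protocol.

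**Conclusion.** The concern holds, and the definition must be corrected. Followed as written, it gives a misleading SAE percentage: serious drug harms are counted but diluted with mild events, and serious events attributed to surgery or fibroids are left out. Those that are also expected go only to annual reports.

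The number of events affected cannot be derived from the protocol. The surgical exclusion spans 30-33% of study time for a woman who has the planned operation. The figure of 6 to 15 women per arm is illustrative and rests wholly on the assumed 20-50% rate. The primary outcome, the tabulation of all adverse events by arm and the telephone reports are unaffected, and written IND reports largely so. The conclusion assumes that the Section 7 definition governs the SAE outcome and reporting, as its wording says.

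**What to change.** Replace the sentence in Section 7 with an outcome-based definition that applies whatever the presumed cause. It should cover at least the fatal and life-threatening outcomes the section already names, and list explicitly any others intended, for example unplanned hospital admission. Record relation to surgery, relation to fibroids, relation to study drug, and expectedness as separate items, none of which decides seriousness.

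Then bring the reporting sentences in Sections 7 and 11.1 into line with the new definition, with one stated route for events that are unexpected but not serious. Revise the opening statement of Section 7 about anticipated SAEs if it no longer fits.

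The cost is one definition, matching wording in two sections, and attribution and expectedness fields if the SAE form lacks them. There may be a few more reports of serious surgical or fibroid events, offset by fewer mild events on the SAE form. Design, sample size and the primary analysis do not change.
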